At week 2 (the end of the 2-week baseline, in person), participants will hand in scores and be randomized to a frequency. Part of this 60-minute visit will be considered standard of care, a level 3, 20-minute educational visit on a commonly used treatment option. They will be given a TENS unit and taught how to use the unit. Teaching will include positioning of electrodes, as well as what buttons they are allowed to manipulate. The TENS unit settings will be pre-determined at the clinic and measures will be taken to ensure that the settings cannot be altered at home. The participant will be instructed not to open the TENS unit during the 2 treatment weeks of the study to ensure the settings are maintained. They will be instructed to continue only their baseline treatments.

Settings: The TENS unit used is a Compass Health TENS 3000, 3 mode Analog Unit. The participants' TENS unit will be set at Normal Mode (N), a pulse width of 200 microseconds and an intensity to be determined in the office based upon when the participant feels sensitive to the TENS unit. Frequency (pulse rate) will be determined by randomization. The participant will place the electrodes along the posterior tibial nerve on the medial ankle with a ground on the inner arch, each day for 30 minutes for a total of 14 days at the time of day typically associated with the worst pain or at the first opportunity for rest after this time.

Group 1 will be the **low** frequency group. This means that the TENS therapy will use a frequency of 20 Hz.

Group 2 will be the **medium** frequency group. This means that the TENS therapy will use a frequency of 50 Hz.

Group 3 will be the **high** frequency group. This means that the TENS therapy will use a frequency of 100 Hz.

Participants will be provided the TENS unit, its manual, and enough patches to last the 2 weeks of the treatment period. Participants will be given a weekly usage log, weekly pain VAS and weekly GUPI questionnaire logs again for 2 weeks they are actively using the TENS, with the option of paper or Qualtrics. In this log, the rating of pain by VAS and GUPI, the rating of genitourinary symptoms by GUPI, duration of TENS therapy, usage for every day of the week and adverse reactions to the TENS unit (rash) will be recorded.

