All subjects will be analyzed according to the intention-to-treat [ITT] principle. A participant will be considered evaluable and will be included in the intention-to-treat analysis if the participant has documented at least 8 sessions of their designated TENS treatment (about 4 times a week of TENS therapy). Analyses that take into account the actual treatment received (e.g., non-compliance, etc.) will be carried out as a secondary analysis (per protocol [PP] analysis).

Primary Statistical Objective:

The primary objective of the study is to compare the three TENS treatment groups after two weeks of active treatment, with respect to:

The change in VAS and GUPI pain questionnaires from baseline to after two weeks of

therapy.

The proportion of responders after two weeks of therapy.

Secondary Statistical Objectives:

Secondary objectives include comparison of the three treatment groups with respect to the rating of VAS and GUPI scores, separately, over time (by weekly diary entries). Analysis will be carried out to determine if there are time-dependent changes in questionnaire scores across the three TENS treatment groups. Urinary symptoms and individual pain site questions will be noted.

Pairwise comparisons of TENS groups will also be carried out to compare each arm with one another using Tukey's multiple comparison tests.

We will again collect data at 1,2-, and 3-months post-trial, asking how much the TENS has been used, to assess durability.

Outcome Variables and Schedule of Assessments:

The primary outcome variable of interest is participant's percentage change in VAS and GUPI from before treatment to the end of 2 weeks of active TENS. Also evaluated will be the response to treatment each week during the 14-day TENS therapy period and the 2 weeks of observation. A participant is said to have a favorable response to the treatment if he/she has a decrease of at least 2 points on the VAS or 1 point on the GUPI question #9 from baseline to after two weeks of TENS therapy. Change in outside interventions will not be permitted during the study but stable therapies will be maintained (e.g., medications).

Demographics and participant characteristics will be collected at baseline (age, gender, medical history, surgical history, current medications, site of pain, duration of chronic pelvic pain). The following outcomes will be measured at baseline, at each week, and at 3 months after the TENS therapy month:

- VAS Weekly Scores
- GUPI Weekly Scores

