Statistical Methods

For the primary objectives:

- Analysis of variance with a fixed effect of treatment with Tukey's multiple comparison test will be used to test for differences in the reduction in genitourinary symptoms among the three treatment arms. Reduction will be parameterized as a relative change from baseline to after the two weeks of treatment. VAS pain response before and after treatment will be compared among the three groups using repeated measures ANOVA with Tukey's multiple comparison tests.
- The Chi-square test or Fisher's exact test, as appropriate, will be used to compare the rates of response among the three treatment arms at the end of the 14-day treatment period.

For the secondary objectives, a repeated measures analysis of variance will be used to analyze the outcomes of interest on a week-to-week basis (improvement in GUPI scores). A treatment-by-time interaction will be examined to determine if the patterns of change in GUPI and VAS scores over time differ across groups. Adjusted pairwise comparisons (Tukey or Bonferroni method) will be used to compare treatment groups to one another.

Data transformations may be applied, if necessary, in order to meet the required standard model assumptions.

Sample Size Considerations

Power: The number of participants needed was based on a power calculation (ANOVA with 2-tailed alpha of 0.05) assuming that the minimally important difference to detect among the three groups in the change in VAS score would be at least one within-group standard deviation of the change in score at 14 days. With 21 participants per group the power is estimated at 81%. We propose to randomize 25 per group assuming the dropout rate may be as high as 20%.

Based on investigator expertise and some published studies, we assume that the proportions of responders based on our criteria of a “favorable response” for each of the three TENS groups will be around 40 % (1,2,4,7,10). In our study we are aiming for at least a 40% response rate in our complex and refractory population.

Conduct of the study

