The principal investigator, [name] MD, is responsible for overall oversight of the data, monitoring the data, assuring protocol compliance, and conducting the safety reviews. The principal investigator will also be responsible for compiling the data sheets, day to day oversight of research and ensuring the integrity and privacy of the data. During the review process the principal investigator, along with the other investigators, will evaluate whether the study should continue unchanged, require modification/amendment, or close to enrollment. The principal investigators or the Institutional Review Board (IRB) have the authority to stop or suspend the study or require modifications.

The master key will house PHI relating to name, address, phone number, MR number and date of birth. The secure Qualtrics survey obtained weekly from participants will be securely downloaded as an excel spreadsheet into a protected AMC Onedrive file accessible only to study personnel. This spreadsheet will be uploaded directly to the secure one drive account to ensure participant confidentiality and security of PHI. Paper surveys will be entered into this database within Onedrive. The master key and database will be stores in separate protected Onedrive files.

Any worsening symptoms or adverse reactions will be reported to the examiners, by way of pain questionnaire, phone calls to participants, the 14-day clinic visits, or reported by participants aside from these instances. For participants with any severe or persistently worsening symptoms or adverse reactions, TENS therapy will be immediately discontinued, they will be removed from the study and considered to have failed treatment and receive medical treatment as necessary. Skin irritation is the most common adverse reaction to TENS units; however, this is mostly associated with allergy to the self-adhesive electrodes (12). While pain may be a

complication with TENS, studies have shown TENS is actually beneficial in treatment of pain over different areas of the body (12).

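### The set called intention-to-treat admits only participants with at least 8 documented TENS sessions, so early stops and low-compliance users drop out of every primary comparison

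*Combined protocol and SAP*

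**What the plan says.** All references are to the combined protocol and SAP.

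- **Section D, Intention-to-treat.** The opening sentence is "All subjects will be analyzed according to the intention-to-treat [ITT] principle". The next sets the operative condition: a participant "will be included in the intention-to-treat analysis if the participant has documented at least 8 sessions of their designated TENS treatment". A per-protocol analysis, which takes account of the treatment actually received, is secondary.
- **Section B, Settings.** TENS is applied "each day for 30 minutes for a total of 14 days", so one session a day is planned.
- **Section D, Primary Statistical Objective and Statistical Methods.** The primary objective covers change in VAS and GUPI and the proportion of responders. For responders, a chi-square or Fisher's exact test "will be used to compare the rates of response among the three treatment arms at the end of the 14-day treatment period".
- **Section D, Conduct of the study.** "For participants with any severe or persistently worsening symptoms or adverse reactions, TENS therapy will be immediately discontinued", and "they will be removed from the study and considered to have failed treatment". Section E also takes participants with skin irritation from the pads off the study.
- **Section D, Sample Size Considerations.** A response rate of around 40% is assumed in each group. On attrition: "We propose to randomize 25 per group assuming the dropout rate may be as high as 20" percent.

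**The concern.** An intention-to-treat set is fixed by randomisation. Here entry depends on how many sessions a participant completes and logs, which is known only after treatment starts and may depend on how treatment is going. Because the per-protocol analysis is secondary, the filtered set carries the primary results, and no analysis of all randomised participants is specified.

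Two things follow. First, the response rates and mean changes would describe people who kept using TENS, not all who were assigned a frequency. Second, the responder endpoint is the only one with a success-or-failure status, yet participants whom the plan itself regards as failures can be missing from its denominator. Two analysts could report different primary response rates from the same data, depending on whether they gave precedence to the 8-session rule or to the failure statement.

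The stopping rule also responds to the outcome: "Any worsening symptoms or adverse reactions will be reported to the examiners, by way of pain questionnaire", among other routes. Exclusion could therefore be related to pain.

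**Working it through.** **Step 1. Who is excluded.** At one session a day (section B, Settings), the 8th session falls on day 8 at the earliest. A stop in days 1 to 7 leaves at most 7 sessions, and 7 < 8. The Intention-to-treat paragraph itself equates 8 sessions with about four a week. At that pace the 8th session falls on day 11 (days 1–4 and 8–11) to day 14 (days 4–7 and 11–14), so for such users stops up to day 10 to 13 are excluded too. Anyone with fewer than 8 of the 14 planned sessions is excluded, whatever the reason.

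**Step 2. Side by side.**

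| Text | Consequence for a participant stopped on day 5 for an adverse reaction |
|---|---|
| Intention-to-treat, first sentence | included |
| Intention-to-treat, 8-session condition | excluded (at most 5 sessions) |
| Conduct of the study | removed, regarded as a treatment failure |
| Responder definition (Outcome Variables) | no rule; needs a score after two weeks of therapy |

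No text says which line prevails. A participant stopped on day 10 with 10 sessions would be in the set, but is off the study with no Week 4 score planned, and again no text says that the failure status means non-response.

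**Step 3. Effect on one arm's response rate.** Inputs: 25 per arm, 40% response and a 20% dropout ceiling (Sample Size Considerations). No early-stop rate is given, so I assume k = 0 to 5 excluded failures per arm. The upper end is 0.20 × 25 = 5, the all-cause ceiling, and is not an estimate of such stops.

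- Reading A: 40% respond among those not stopped. Excluding stops gives 40.0%; counting them as failures gives 0.40 × (25 − k)/25.
- Reading B: 40% applies to the whole arm, 10 of 25. Counting stops as failures gives 40.0%; excluding them gives 10/(25 − k).

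| k | A: counted as failures | A: overstatement | B: excluded | B: overstatement |
|---|---|---|---|---|
| 0 | 40.0% | 0 | 40.0% | 0 |
| 1 | 38.4% | 1.6 | 41.7% | 1.7 |
| 2 | 36.8% | 3.2 | 43.5% | 3.5 |
| 3 | 35.2% | 4.8 | 45.5% | 5.5 |
| 4 | 33.6% | 6.4 | 47.6% | 7.6 |
| 5 | 32.0% | 8.0 | 50.0% | 10.0 |

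Per omitted failure this is 1.6 points under A, and 1.7 to 10.0/5 = 2.0 points under B.

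**Step 4. Effect on the comparison between arms.** I simulated 25 per arm with a true response of 40% in every arm, all stops non-responders, and a chi-square test at nominal 5%. The stop rates are assumptions.

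| Early stops by arm | Rejection, stops excluded | Rejection, stops counted as non-response |
|---|---|---|
| 20/20/20% | about 5% | about 5% |
| 0/4/8% (0, 1, 2 of 25 on average) | about 5.5% | about 5% |
| 0/0/20% (ceiling in one arm only) | about 10% | about 5% |

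Equal stopping does not distort the test. A difference of a participant or two between arms does very little.

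**Step 5. The plan's own power figure.** The stated 81% with 21 per group reproduces: a three-group ANOVA with means at −0.5, 0 and +0.5 SD has noncentrality 21 × (0.25 + 0 + 0.25) = 10.5 and power 0.815. The point here concerns who is analysed and does not depend on that figure.

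**The case against.** **The failure statement may override the 8-session rule.** It is the more specific text, it sits in the same section, and the Intention-to-treat paragraph opens by covering everyone. Alternatively, it may be only a clinical disposition, since it names no endpoint and is followed by a provision for medical care. Either reading is possible. What stands is that the texts are not reconciled. A reader should not infer that the plan definitely drops these failures, nor that it already defines them as non-responders. On either reading, ordinary low-compliance users remain excluded from a set called intention-to-treat.

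**The numbers may be tiny.** This is a fair point. Section F describes side effects as very rare, adhesive allergy is an exclusion criterion, and intensity is set to tolerance. A reader might take the 10-point figure in the table as the expected overstatement. The documents do not support that: it applies the all-cause dropout ceiling to a single cause.

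**The trial compares arms, not absolute rates.** A reader might infer that the frequency comparison is biased. That needs stopping to differ by arm. Conduct of the study attributes most dermatitis to the pad adhesive, which gives no reason to expect a difference for skin reactions. Worsening pain could differ if the frequencies differ in effect, but the documents do not show that they do. Forms are weekly, so persistent worsening would also be hard to establish from them within the first week.

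**Conclusion.** The plan contradicts itself as written: it applies the name intention-to-treat to a set restricted by compliance after randomisation, and that set serves the VAS and GUPI change analyses as well as the responder comparison. The exclusion of day 1 to 7 stops follows directly from one session a day.

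The size is unknown. Assuming 25 per arm and 40% response, each omitted failure overstates an arm's response rate by roughly 1.6 to 2 points. Bias between arms is conditional on unequal stopping and is small unless stops are both common and unequal. The change should be made because of the mislabelled set and the unlinked failure status, not because a large bias has been shown. Confidence is high in the textual conflict and low in any particular magnitude.

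**What to change.** 1. **Intention-to-treat.** Define the ITT set as all randomised participants, analysed by assigned frequency. Use the 8-session criterion only for the per-protocol set, which is already planned.
2. **Responder analysis.** Count every participant whose TENS is stopped for worsening symptoms or any adverse reaction, including pad irritation, as a non-responder. This should be one rule with no sorting by severity. The documents give no criterion for separating skin reactions into two scoring classes, and only participants and caretakers are stated to be blinded, so staff who may know the frequency should not have to decide.
3. **Conduct of the study and section E.** Replace removal from the study with discontinuation of TENS, and keep requesting the existing weekly VAS and GUPI forms through Week 4. These participants then contribute observed scores to the change analyses. The rules for stopping TENS stay as they are.

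The cost is amendment wording and up to two more weeks of existing forms for those who stop. Section B already allows the 7-day and 14-day visits to be virtual. The reported response rate may be slightly lower. Some Week 4 scores may still be missing, and the plan should say how the change analyses handle them.

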Participants may be called during the 14-day treatment period to keep on track, address any concerns, questions, or any adverse reactions to TENS therapy by the physician or research staff. Their phone numbers will be maintained in the master key associated with the deidentified database in the AMC Onedrive protected research file for this purpose.

At 7 days and the end of the 14-day treatment period the visit can be performed either virtually or in the office. The 7-day visit will be considered purely a study visit and the 14 day visit a standard of care visit.

The completed week 3 and 4 VAS and GUPI, treatment usage documents will be returned. The participants will also be asked the question "Will you continue using TENS therapy for your pelvic pain?" Any persistent issues will be addressed during these visits as well and further options discussed.

For those who would like to continue the TENS unit, participants will be taught how to adjust settings and sites at home. Participants will be given repeat VAS and GUPI at 1, 2, and 3 months post-initial phase and seen again at 3 months as part of standard care. Here we will review logs of what frequency patterns they developed with TENS usage on their own, if any. In this time participants may increase or decrease the frequency of their device anywhere in the range of 2 Hz to 150 Hz to see which they prefer most in this part of the trial. Participants will also be allowed to adjust pulse width (30 to 260 μ S), mode (B N M), time (continuous, 15, 30 minutes), and intensity (1 to 8, 10-80mA) as desired. The only requests will be that they remove the device if any discomfort occurs and that they log their settings versus their response.

Note:

TREATMENT MODE (B, N, M):

Normal (Continuous, Conventional) TENS offers the practitioners complete control over all the various treatment parameters of the instrument. **Burst** Mode is analogous to the Low Rate TENS technique except the low frequency individual pulses are replaced by individual "bursts" of 7-10 individual pulses. It is thus a combination of Conventional TENS and Low Rate TENS. In Burst Mode, the treatment frequency is fixed by the instrument and is not adjustable with the Frequency Rate control. Participants will be educated about this. **Modulated** Mode attempts to

Version Date: 5/14/2022

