Participants with contraindications to TENS (eg, other electrical devices, pregnancy, bleeding or clotting disorders, unhealthy tissue, seizure disorders, malignancy, impaired cognition, adhesive allergy) will be excluded from the study. Participants will be taught safe practice with the use of a TENS unit, such as performing a sensory discrimination test in the office, checking and cleaning skin before starting a TENS session, monitoring skin for signs of irritation, changing adhesive on electrode pads after each use, securing electrodes with even pressure distribution and full contact, and watching for signs of TENS unit malfunction requiring maintenance [11].

Participants will be instructed to adjust the intensity to the level they can tolerate, so if the TENS intensity is too high then the participants will not be able to tolerate. Pain is the main issue with increased intensity (when it is not used to actually treat pain), therefore intensity will be minimized as per protocol to prevent this (“to the participant’s perception and tolerance”). Increased intensity would be assumed to lead to skin break down, however, reports of this are exceedingly rare (13). Participant education will be comprehensive here.

While reports of dermatitis have been reported in the literature, in most of these cases the dermatitis is caused by an allergy to the adhesive on the TENS electrode pads and not the actual electrical stimulation. Skin irritation can occur, but this is mostly seen in cases where TENS therapy has been used for multiple hours in a row. There has been only one case report in the literature (and not even searchable in Pubmed) of an actual burn from a TENS unit (14). In contrast, TENS therapy is actually used for pain relief on burn participants. Therefore, the risk of being burned from TENS therapy is extraordinarily low.

The effects of prolonged TENS usage have been studied in the literature before. The meta-analysis by Mark Johnson et al showed TENS units to be very safe with very few adverse effects seen even for more extended periods of use (10)

E. RISKS

The risks are minor and unanticipated. If there is any irritation to the participants skin due to the adhesive pads the participant will be treated and taken off the study.

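### The analysis labelled intention-to-treat admits only participants with at least 8 documented sessions, and the plan contains no analysis of everyone randomized

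*Combined protocol and SAP*

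**What the plan says.** Section D, under Intention-to-Treat, opens with "All subjects will be analyzed according to the intention-to-treat [ITT] principle". The next sentence narrows this: a participant counts as evaluable and is "included in the intention-to-treat analysis if the participant has documented at least 8 sessions of their designated TENS treatment". A per-protocol analysis reflecting treatment actually received is named separately, as secondary.

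Under Settings in section B, TENS is applied "each day for 30 minutes for a total of 14 days". The primary outcome is the change from before treatment to the end of those two weeks, and the response definition uses the same time point.

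Two passages take participants out. Under Conduct of the study (section D), for those with serious or continuing deterioration or adverse reactions, TENS is stopped and "they will be removed from the study and considered to have failed treatment and receive medical treatment as necessary". Section E (Risks) adds: "If there is any irritation to the participants skin due to the adhesive pads the participant will be treated and taken off the study".

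Statistical Methods says nothing about how removed participants, or those without a two-week score, enter any test.

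**The concern.** Sessions accrue after randomization, so a minimum-session rule selects on behaviour that the assigned frequency and its effects can influence. Such a set is a compliance set, whatever it is called. A comparison among people who kept using TENS would be reported as intention-to-treat, and no other planned analysis includes everyone randomized.

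This matters because the trial's aim is to name the best of three frequencies. If one frequency provokes more early worsening or pain, dropping those participants makes that arm look better than it is. If early failures are equally common in all arms, the ranking is not distorted, but every arm's response rate is overstated.

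A second gap is separate. Someone stopped after session 10 passes the 8-session rule, yet may have no Week 4 score if follow-up ends on removal.

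**Working it through.** **Who the rule excludes.** Planned sessions: 14, one a day. Required: 8, and 8/14 = 57%. A participant on schedule who is stopped before day 8 has at most 7 sessions and is out. So is someone who uses the unit every other day (14/2 = 7).

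**Does the failure statement repair this?** It stands under Conduct of the study. The Intention-to-Treat paragraph and Statistical Methods neither repeat it nor say which rule wins when a failed participant has fewer than 8 sessions. It also supplies no value for the change in VAS or GUPI.

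**The plan's own figure.** One-way ANOVA, three groups of 21, alpha 0.05, means at 0, 0.5 and 1 SD (Cohen's f = 0.408): the noncentral F distribution gives power of 81.5%, against the stated 81%. The power figure is not in dispute.

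**Effect on a response rate.** Inputs: 25 per arm and about 40% response (Sample Size Considerations), so 10 responders. Assume that early failures are non-responders and that the failure statement is not applied. The rate with k of them left out is 10/(25 − k):

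| k | Rate | Shift |
|---|---|---|
| 0 | 10/25 = 40.0% | – |
| 1 | 10/24 = 41.7% | 1.7 points |
| 2 | 10/23 = 43.5% | 3.5 points |

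The standard error of one arm's rate is √(0.40 × 0.60 / 25) = 0.098, or 9.8 points. Two arms with equal true response and 2 versus 1 early failures would show a false difference of 10/23 − 10/24 = 1.8 points.

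**Effect on ranking and test.** Simulation of 40,000 trials: 25 per arm, 40% response in every arm, early failure in 4% of two arms and 8% of the third, all early failures non-responders. These early-failure rates are assumptions; the documents give none.

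| Analysis | 8% arm ranks highest | Chi-square rejects |
|---|---|---|
| All randomized | about 33% | about 5% |
| 8-session set, all failures stop before session 8 | 38.2% | 5.2% |
| 8-session set, half stop before session 8 | 36.1% | 5.0% |

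**Cost of including everyone.** With all 25 per arm, ANOVA power is 88.3% if the 1 SD effect is undiluted. If 10%, 16% or 20% of each arm contribute no difference between frequencies (assumed), it is 80.3%, 74.3% or 69.8%.

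**The case against.** Four points on the other side have force.

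First, the statement that removed participants failed treatment can fairly be read as a non-responder rule. If it governs, most of the inflation of the response rate disappears for that group. This stands as a limit on the size. It does not settle the matter, because the plan never reconciles it with the 8-session rule and it offers nothing for the change scores. Participants taken off only for adhesive irritation under section E are not described as failures there.

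Second, a reader might infer that every removed participant lacks a Week 4 score. The documents do not support that. The plan says "At 7 days and the end of the 14-day treatment period the visit can be performed either virtually or in the office", Week 4 questionnaires are returned then, and worsening may be detected at that same visit. For earlier removals, the missing score is inferred from removal and from the absence of any later scheduled collection.

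Third, a reader might infer that the rule always flatters an arm. That is not shown for people who simply use TENS little. Some may do so because they improved, and leaving out responders lowers the rate. The documents also give no reason for adhesive irritation to differ by frequency.

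Fourth, large distortions can be produced by assumption. With early failure of 4%, 12% and 20% across the arms, chi-square rejection rises to 7.4%. Nothing in the documents supports such rates; the plan expects few adverse effects. The 40% figure is also only an aim ("In our study we are aiming for at least a 40% response rate in our complex and refractory population"), with no test attached, so the rule does not decide whether the trial succeeds.

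**Conclusion.** The concern holds. The set called intention-to-treat is a post-randomization adherence set that contradicts the sentence before it, and nothing elsewhere in the plan corrects this. The failure statement is not carried into the response test, and no rule covers missing Week 4 scores.

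The likely size is small: 1.7 to 3.5 points on an arm's response rate for one or two early failures, if the failure statement is not applied. In the 8% versus 4% illustration, the arm with more failures ranks highest in about 38% of trials instead of 33%, and the test's error rate is close to nominal. These figures rest on assumed early-failure rates and on early failures being non-responders. The direction for low users is unknown.

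The documents do not support reading this as a threat of frequent false-positive findings. The harm is mainly to the estimates, the ranking and the label. The change should be made while participants are still being followed, since scores not collected after removal cannot be recovered.

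**What to change.** 1. **Analysis sets (section D, Intention-to-Treat).** Define intention-to-treat as every participant randomized at the Week 2 visit, in the assigned arm, whatever the number of sessions. Use the 8-session minimum to define the per-protocol set already planned.
2. **Response test (Statistical Methods).** Use all randomized as the denominator. Count participants removed under Conduct of the study as non-responders. Treat others without a Week 4 score as non-responders by a stated convention, which is a choice and not a requirement of intention-to-treat, and add a sensitivity analysis.
3. **Removal wording (Conduct of the study; section E).** Replace removal from the study with stopping TENS while the Week 3 and Week 4 questionnaires continue, by phone or Qualtrics, unless consent is withdrawn. Record any rescue treatment.
4. **Change scores.** Analyse all randomized participants with available scores, using a mixed model for the weekly data. Add one sensitivity analysis that gives those removed for worsening an unfavourable value.
5. **Reporting.** Give removals, reasons and sessions completed by arm.

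The cost is a rewritten paragraph, a few lines in Statistical Methods, one changed sentence in each removal passage, and at most two remote questionnaires per stopped participant. No extra visits or participants are needed. The downside is that low-use participants may dilute differences between frequencies; the per-protocol result remains available to show this.
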